1.0 OVERVIEW

Nephrotic syndrome is the most common acquired kidney disease in children.¹ Affected children have recurrent episodes (or relapses) of proteinuria that may lead to life-threatening complications including sepsis, peritonitis and thromboembolism.² The goals of treatment are to induce remission of proteinuria, reduce the number of relapses, minimize toxicity of treatments and delay kidney damage.³ The first-line treatment for nephrotic syndrome is oral steroids, and many children will need repeated courses of steroids for relapsing disease.^{2,4} However, steroid treatment is associated with many side effects, including obesity, growth retardation, hypertension, cataracts, poor bone health, and cosmetic effects.^{2,5-15} Various other non-steroid immunosuppressive drugs are often used in the course of illness to decrease frequency of relapses and to avoid side effects of prolonged and recurrent steroid use.¹⁶ Treatment protocols for relapsing nephrotic syndrome are therefore complex, requiring multiple drugs and multiple courses of therapy over long periods of time for disease control.

International clinical practice guidelines are available to guide treatment of nephrotic syndrome;¹⁷ however, many of the recommendations are based on poor quality evidence and very few randomized controlled trials - leading to considerable debate among physicians regarding best treatment approaches.^{18,19} As a result, drug treatment protocols and processes of care for childhood nephrotic syndrome are highly variable among physicians and care centres; evidence practice gaps also exist.^{20,21} In a survey of Canadian pediatric nephrologists, we found striking variation in dose and duration of steroids and second line agents reportedly used for first presentation and relapses of nephrotic syndrome.²² Lack of consensus between physicians and centres regarding best treatment approach can lead to a frustrating experience for patients and families, poor satisfaction with clinical care, and sub-optimal outcomes.^{19,23} Using a priority setting survey, we identified that addressing these issues in the management of childhood nephrotic syndrome is the top priority for the Canadian pediatric nephrology community.

In Canada, little research has been done to evaluate and improve outcomes of children with nephrotic syndrome. It is not known whether variability in treatments affects patient outcomes – addressing this problem is a necessary first step towards improving care and patient experience. A carefully constructed prospective longitudinal cohort with a large and generalizable sample of patients can help us answer this question. Therefore, we have established the first national prospective cohort of children with nephrotic syndrome with the overall goal to provide *best care based on best evidence*.

Over the last 2 years, we received start-up funds from Canadian Institutes of Health Research (CIHR) and other sources to establish this cohort in 13 sites across Canada. We have enrolled 77 patients to date and have provided our preliminary data in this application. The funds received to date are inadequate to reach the sample size needed and to complete the observation period required to address the research questions as proposed *within this* application. We have noted in the proposal and budget, the progress of our ongoing work and where new funds are needed. We have also carefully considered past review committee comments in this re-submission.

We will use the prospective cohort to address the following 2 objectives:

Objective 1

[figure not shown]
- a) To determine the association of steroid dose prescribed (total dose prescribed during observation period divided by total number of days on treatment) and relapse rates (primary outcome defined as total number of relapses divided by total observation time).

Objective 2

- a) to determine the associations between centre-, physician-, patient-level characteristics and i) steroid dose prescribed, and ii) length of steroid treatment for first presentation and subsequent relapses of nephrotic syndrome;

- b) To identify reasons for practice variation in treatments for nephrotic syndrome between and among pediatric nephrology care providers and centres.

For Objective 1, we will evaluate association of steroid dose prescribed with relapse rates, adjusting for patient characteristics. For objective 2, we will use multi-level modeling with patients nested within physicians and physicians nested within health centres, to evaluate the association of patient-, physician- and centre-related factors with variability in steroid treatment dose prescribed. An embedded qualitative study utilizing focus groups of health care providers will enrich the quantitative results by providing an understanding of attitudes, beliefs and local factors driving variation in care at participating centres, while considering provider characteristics (training background, experience) and centre characteristics (use of standardized protocols). Quantitative and qualitative results will be integrated (using a convergent parallel mixed methods design) for interpretation at the end of study, and collectively inform strategies for development and implementation of best practice treatment protocols across centres to improve overall provision of care in this patient population. *See adjacent figure for overview of study.*

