2.3 Steroid treatment protocols used for nephrotic syndrome today were developed over 40 years ago, and revised over time. These protocols were drafted as part of an international cohort study of children with nephrotic syndrome (International Study of Kidney Disease in Children, ISKDC) between 1967-1974, with the aim to induce remission of proteinuria and reduce risk of relapses.³⁴ Later in the 1980s and 1990s, clinical trial evidence generated by the German working group for pediatric nephrology supported that longer initial courses of steroid therapy led to fewer relapses over time.^{38,39} As a result, many Canadian pediatric nephrology physicians and centres changed their steroid protocols from the original ISKDC regimen of 4 weeks of daily steroid therapy followed by 4 weeks of alternate day therapy to 6 weeks of daily steroid therapy followed by 6 weeks of alternate day therapy for first presentation of nephrotic syndrome (total therapy time increased to 3 months from 2 months). More recently, the results of a meta-analysis published in 2007 suggested prolonging therapy up to 6 months for first presentation of nephrotic syndrome may decrease the number of relapses over time compared to 3 month regimens⁴⁰ - prompting some physicians to adopt 6 month steroid protocols.

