2.4 Although a reasonable body of evidence is available to guide practice, practice variation is common in nephrotic syndrome. The available evidence base for treatment of first presentation and relapses of nephrotic syndrome were synthesized and published in several systematic reviews, local guidelines,^{2,40,41} and also in a recent international clinical practice guideline.⁴² Nevertheless, lack of consensus regarding best treatment approaches is a well-known international phenomenon. Variation in care was documented in surveys of American pediatric nephrologists in 2000 and 2009; however, little has been done to address this problem in the United States or elsewhere.^{20,21} We performed a similar survey which was sent to all Canadian pediatric nephrologists (n=58) and achieved a 69% response rate. The results showed significant variation in steroid protocols and also in the choice of steroid sparing drugs and biopsy practices (see manuscript attached, [name] S, *Pediatr Nephrol* 2013). The total duration of steroid therapy ranged from a minimum of 7.5 weeks to a maximum of 26 weeks (median 16 weeks) for first presentation of nephrotic syndrome – likely contributing to considerable variation in cumulative steroid exposure among patients who may otherwise have similar clinical presentations. Sample protocols used by Canadian physicians and centres are shown in Appendix Tables 1a and 1b. The overall impact of this variability in steroid exposure on relapse rates of Canadian children with nephrotic syndrome has not been formally assessed and remains the most important and compelling unanswered question.

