Privacy and confidentiality: We will assign unique study numbers to patients, physicians and centres – to protect anonymity of all participants and centres. All identifying information will be securely stored at individual sites and will not be shared with central study staff.

Characterizing the cohort: We will describe (using means with standard deviation, medians with interquartile range and proportions as appropriate) the cohort demographics, and all outcomes of interest by centre-, physician, and patient- level variables. We will describe the following outcomes: overall steroid prescribed (total dose and number of treatment days), time to first relapse, relapse rate during observation, time to steroid sparing agents, choices of steroid sparing agents and indication, time to kidney biopsy, reasons for biopsy, complications of steroid therapy. Outcomes related to complications of steroid treatment will include: anthropometric changes during observation period (age- and sex-specific standard-deviation scores (z scores) for height, weight, and body-mass index); persistent systolic/diastolic blood pressure $\geq 95^{\text{th}}$ percentile during observation period [yes/no] and requirement for antihypertensive therapy [yes/no] and duration of therapy; and external manifestations of steroid toxicity evident during semi-annual study visits (Cushingoid faces [yes/no], hypertrichosis [yes/no], cataracts [yes/no], striae [yes/no], acne [yes/no]). Definitions of external manifestations of steroid toxicity are

similar to those observed in prior nephrotic syndrome steroid dosing studies.³⁸ See Appendix, Table 4 for detailed description of these variables.

3.2 Work plan for objective 1

Design: To determine the association of steroid dose prescribed with relapse rates, we will use the prospective cohort as described in section 3.1. We hypothesize that increasing steroid dose prescribed per unit time will be associated with decreasing relapse rates. All patients with steroid sensitive nephrotic syndrome enrolled into the prospective cohort will be eligible for this study. The observation period will span a maximum of 4 years and minimum of 6 months. Figure 4 in the Appendix provides a visual representation of the outcome and exposure as defined below for this objective.

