Outcome: The primary outcome of interest is relapse rate (number of relapses/per person unit time). Relapse rate is the most clinically relevant outcome for nephrotic syndrome and the best indicator of morbidity experienced by patients; this outcome definition is consistent with prior literature in this area.⁴⁰

Exposure: The exposure is steroid prescribed per unit time - that is the total dose patients were prescribed as treatment for episodes of proteinuria divided by the sum of duration of 'days on steroids' during observation period. Days on steroids is defined by the sum of the length in days of all episodes (see definition of episode in section 3.1, also graphically represented in Appendix Figure 4) observed. This definition is consistent with measures of steroid exposure used in prior nephrotic syndrome steroid dosing studies conducted in Europe and in a Canadian study of steroid associated osteoporosis in children.^{38,55} Systemic steroid exposure (both oral and intravenous) will be converted into prednisone equivalents (mg/m^2) using standard dose conversion tables and weight based dosing criteria [mg/kg] will be converted to mg/m^2 .

Analysis plan: The unit of analysis is the patient. Given that the main outcome of interest is relapse rate, we will use Poisson regression models with steroid prescribed per unit time as the exposure and relapse rate per unit time as the outcome, adjusting for patient level variables (age, gender, ethnicity, household income, parental education) and episode at entry into study (either first presentation, first relapse or second relapse), and taking into account time at risk. We are not using multi-level (hierarchical) analysis in this objective, as there is no clustering at the patient-level. There is only one measurement per patient, relapse rate adding all episodes experienced by one patient as a count.

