7.0 SUMMARY AND SIGNIFICANCE

Funding the Canadian Childhood Nephrotic Syndrome Project will address important unanswered questions in childhood nephrotic syndrome – what is the impact of variability in steroid treatments on patient outcomes (Objective 1) and who and what drives variability in care (Objective 2)? The integrated results of the study will allow us to develop best practice approaches for treatment of nephrotic syndrome and to develop an implementation plan to ensure uptake of our study results nationally and internationally. This study will provide key information to strategically prioritize future clinical trial questions (what to study, in which patients, when, and how to get buy-in from key stakeholders), and will build basic research infrastructure needed to conduct these trials to address critical knowledge gaps in the treatment of nephrotic syndrome. The novel national longitudinal web based patient data collection system developed as part of this study will also provide a platform to evaluate clinical care and outcomes on an ongoing basis in the future, and ultimately create a best practice approach to treatment of nephrotic syndrome.

REFERENCES

4. Arneil GC. Treatment of nephrosis with prednisolone. *Lancet*. Apr 14 1956;270(6920):409-411.

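### Objective 1 relates relapse rate only to steroid dose per treated day, so no stated analysis relates course length or total course dose to relapse, although the protocol's own question rests on them

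*Protocol*

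**What the plan says.** Section 1.0 defines the Objective 1 exposure as "total dose prescribed during observation period divided by total number of days on treatment". Section 3.2 (Exposure) repeats this and fixes the denominator: "Days on steroids is defined by the sum of the length in days of all episodes". The hypothesis in Section 3.2 (Design) matches: "We hypothesize that increasing steroid dose prescribed per unit time will be associated with decreasing relapse rates". The Poisson model in Section 3.2 has this one steroid term. It adjusts for age, gender, ethnicity, income, parental education and the episode at entry.

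The rationale is about how long children are treated. Section 2.3 recounts a change in many centres from "4 weeks of daily steroid therapy followed by 4 weeks of alternate day therapy to 6 weeks of daily steroid therapy", followed by six weeks of alternate-day treatment, and a later move by some physicians to six months. Section 2.4 reports from the Canadian survey: "The total duration of steroid therapy ranged from a minimum of 7.5 weeks to a maximum of 26 weeks". It links this to differences in cumulative exposure, then says: "The overall impact of this variability in steroid exposure on relapse rates of Canadian children with nephrotic syndrome has not been formally assessed", and ranks that gap above all others. Section 7.0 words the question as "what is the impact of variability in steroid treatments on patient outcomes (Objective 1").

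Total dose and duration appear in two other places. Section 3.1 (Characterizing the cohort) lists "overall steroid prescribed (total dose and number of treatment days") among the items to be described. Section 3.3 models total dose, average daily dose and length per episode as outcomes, explained by centre, physician and patient factors.

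**The concern.** A ratio of dose to treated days measures intensity. A longer course adds to numerator and denominator together, so it can leave the ratio unchanged while total dose rises substantially. The variation that Section 2.4 documents is variation in length, with its consequence for cumulative dose. The trials that Section 2.6 says the cohort should complement compare three with six months of treatment.

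As written, Objective 1 can say whether more steroid per treated day goes with fewer relapses. It cannot say whether longer or larger courses do, which is part of the question in Sections 2.4 and 7.0. Section 6.0 feeds the association between treatment variability and relapse into best-practice approaches, so a per-day coefficient should not be taken there as an answer about more steroid in general.

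A second feature limits what the coefficient can mean. Exposure and relapses are accumulated over the same period, and each treated relapse adds a course to the exposure.

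**Working it through.** **The plan's own figure.** Section 3.2 gives a detectable rate ratio of 0.989 at 90% power, two-sided alpha 0.05. Its inputs are mean dose 30.64 mg/m², SD 8.85, base rate 1.68 per person-year, 2 years of follow-up and R² 0.2; the sample is 597. A Wald formula with the variance under the alternative is N = (z₀.₉₇₅ + z₀.₉₀)² × V / [T × rate × b² × (1 − R²)], with V = exp[−(bμ + b²σ²/2)]/σ². Reading 1.68 as the rate at dose zero, N = 597 gives a detectable ratio of 0.9893, and power at 0.989 is 91.3%. The figure reproduces on that reading. It refers to dose per treated day only.

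**Single course.** Take d days daily at dose D, then d days of alternate-day treatment at dose A.
- Total dose = D×d + A×d/2, and days = 2d.
- Exposure = (D + A/2)/2, which does not contain d.

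D = 60 mg/m² is the full dose in Section 3.1. A is not in the visible text. Values of 30, 40 and 60 are assumed for arithmetic only.

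| A | 4+4 weeks: total, per day | 6+6 weeks: total, per day |
|---|---|---|
| 30 | 2100, 37.5 | 3150, 37.5 |
| 40 | 2240, 40.0 | 3360, 40.0 |
| 60 | 2520, 45.0 | 3780, 45.0 |

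For A = 40: (60×28 + 40×14)/56 = 40.0 and (60×42 + 40×21)/84 = 40.0. The total dose ratio is 1.5 in every row, and the equality holds for any D and A.

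**Survey range.** If courses of 7.5, 16 and 26 weeks (the survey minimum, median and maximum) all ran at the protocol's mean of 30.64, their totals would be 52.5×30.64 = 1609, 112×30.64 = 3432 and 182×30.64 = 5576 mg/m². That is a 3.5-fold range of total dose at one exposure value.

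**Pooled over episodes.** The exposure sums all episodes, so exact equality is lost. Assume 200 relapse-treatment days at 30.64 (6128 mg/m²) and A = 40:
- 4+4: (2240 + 6128)/256 = 32.69
- 6+6: (3360 + 6128)/284 = 33.41

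The difference is 0.72, or 0.08 of the SD of 8.85. Over A = 30 to 60 and 100 to 300 relapse days it runs from 0.42 to 1.40, at most 0.16 SD. A 50% longer and larger entry course barely moves the exposure.

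**Dependence on relapse.** On the same assumptions, a child on 6+6 with no relapse scores 3360/84 = 40.0. With 200 relapse-treatment days the same child scores 33.41. The change of −6.6 comes from relapsing alone. Its sign and size depend on how intense relapse courses are compared with the entry course, which the visible text does not give. Section 3.2 gives 30.64 as the mean for the whole exposure, and applying it to relapse days is an assumption.

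**The case against.** The exposure is defined consistently in Sections 1.0 and 3.2, matches the stated hypothesis, is the quantity powered, and is said to follow earlier steroid dosing studies. Sections 2.4 and 7.0 are background and closing prose, and dose per day is one facet of variability. Secondary exposures are often left to a statistical analysis plan, which is not at hand. Much of this stands. The definition is not an error, and the absence of a secondary model would not by itself be a finding. What remains is that the protocol assigns Objective 1 a wider question than its one stated exposure can address.

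Some stronger readings are tempting but not supported.
- A reader might infer from Section 3.3, which mentions cumulative exposure alongside relapse rate, that the protocol contradicts itself. There, cumulative most naturally contrasts with per episode, meaning summed over episodes. It does not promise a model on total milligrams.
- A reader might infer that length pushes the exposure up or down at random. With A = 40 and 200 relapse days, a 26-week course split 4+22 scores 28.5 and one split 13+13 scores 35.1, against 33.4 for 6+6. That reversal comes from the assumed daily/alternate-day split, which is a change in intensity and is what this exposure should detect.
- In the other direction, a reader might infer that the exposure is at least a clean test of its own hypothesis. It is not, because relapses during observation alter it.

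**Conclusion.** The point holds as a gap between question and exposure, and closing it is a worthwhile, inexpensive improvement. Objective 1 can speak to dose per treated day. It says little about course length or total course dose, and the protocol states no other analysis that relates either to relapse. The firmest figure is that the two regimens named in Section 2.3 score identically as single courses despite a 50% difference in total dose. That needs only equal phase lengths within each course and common phase doses. The pooled figures, and any expressed in SDs, are illustrations that rest on an assumed alternate-day dose, assumed relapse days and a borrowed mean. The dependence of the exposure on relapse follows from its definition, but its direction and size cannot be fixed from the protocol.

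**What to change.** 1. In Sections 3.2 and 7.0, state that conclusions from the present exposure concern dose per treated day only. Note that it is accumulated over the same period as the relapses, so relapses alter it.
2. Add two secondary Objective 1 exposures, in separate models because they are correlated: the prescribed length and the prescribed total dose (mg/m²) of the entry course, both as set at its start. Count relapses, including those during taper, and time at risk from that prescription. Adjust for entry type, and show first-presentation entrants separately, since they are the group that the three- versus six-month trials in Section 2.6 address.
3. Do not substitute cumulative dose over the whole period, because each relapse adds a course. Do not use realised episode length either: under the episode definition in Section 3.1, a relapse during taper that restarts full-dose treatment ends the episode.
4. Confirm that the entry form records the planned course. Section 3.1 promises prescription details at entry, but the visible text does not say whether planned length is included.

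The cost is a limiting statement and one or two models. If planned length is not recorded, one field must be added, and the 77 patients already enrolled may lack it. Precision falls in the first-presentation subset. If that subset is one third to two thirds of 597 (an assumption; 199 to 398 patients), standard errors are about √(597/199) = 1.7 to √(597/398) = 1.2 times those in the whole cohort.

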2.0 DISEASE BURDEN AND MANAGEMENT ISSUES

2.1 Childhood nephrotic syndrome is characterized by severe proteinuria, hypoalbuminemia and edema.¹ The incidence rate of nephrotic syndrome is 2 to 7 cases per 100,000 children per year and prevalence is estimated as 16 per 100,000 children.^{1,24-26} In Canada, approximately 150 children will be diagnosed with nephrotic syndrome each year and there are an estimated 1,000 prevalent patients (data collected from participating sites, see attached support letters). Although the cause of this disease is unknown in most children, nephrotic syndrome can occur in association with genetic mutations in the components of the glomerular filtration barrier, comorbid conditions or environmental triggers.¹ Without treatment, children with nephrotic syndrome develop edema-related complications, pleural effusions, severe infections (e.g. peritonitis, pneumonia, sepsis), thromboembolism and eventually, progress to kidney failure or death.²⁷⁻²⁹ Most (70-90%) children with nephrotic syndrome will have a relapsing course of proteinuria (range of 1 to >20 relapses during childhood) leading to significant morbidity.^{10,30} Therefore, nephrotic syndrome is associated with substantial health system costs which include specialist and multi-disciplinary health care team visits, hospital admissions for control of edema, infection or thrombosis and for kidney biopsies.³¹

2.2 Steroids are the treatment of choice for first presentation and subsequent relapses of nephrotic syndrome. Clinical response to steroids is the most important predictor of disease course.² Steroid sensitive patients typically respond to treatment with remission of proteinuria within 2 weeks of therapy and maintain normal kidney function. Steroid resistant patients, defined as those who fail to achieve complete remission of proteinuria after 8 weeks of steroid therapy, have a high risk (>50% in 5 years) of kidney failure.^{32,33} Approximately 90% of children with nephrotic syndrome are steroid sensitive, and they will be the focus of our study.^{34,35} Among these patients remission is achievable with steroid treatment; however, relapses are common requiring multiple courses of steroids and steroid sparing immunosuppressive drugs - leading to significant side effects drug toxicity. Of the children who relapse, up to 50% will have frequent relapses (≥ 2 relapses within 6 months of first response or ≥ 4 relapses in any 12 month period) or become steroid dependent (2 consecutive relapses during tapering of steroid therapy, or relapse within 14 days of steroid cessation).^{10,30} Steroid toxicity reported in children with nephrotic syndrome includes growth retardation and obesity,^{7,9,13,36} hypertension,^{11,37} posterior sub-

capsular cataracts,^{6,12} decreased bone mineral density,^{14,15} and impaired glucose tolerance.⁸ Minimizing relapse rates and steroid exposure are the most important goals in caring for these patients and remain the most relevant clinical outcomes.

2.3 Steroid treatment protocols used for nephrotic syndrome today were developed over 40 years ago, and revised over time. These protocols were drafted as part of an international cohort study of children with nephrotic syndrome (International Study of Kidney Disease in Children, ISKDC) between 1967-1974, with the aim to induce remission of proteinuria and reduce risk of relapses.³⁴ Later in the 1980s and 1990s, clinical trial evidence generated by the German working group for pediatric nephrology supported that longer initial courses of steroid therapy led to fewer relapses over time.^{38,39} As a result, many Canadian pediatric nephrology physicians and centres changed their steroid protocols from the original ISKDC regimen of 4 weeks of daily steroid therapy followed by 4 weeks of alternate day therapy to 6 weeks of daily steroid therapy followed by 6 weeks of alternate day therapy for first presentation of nephrotic syndrome (total therapy time increased to 3 months from 2 months). More recently, the results of a meta-analysis published in 2007 suggested prolonging therapy up to 6 months for first presentation of nephrotic syndrome may decrease the number of relapses over time compared to 3 month regimens⁴⁰ - prompting some physicians to adopt 6 month steroid protocols.

2.4 Although a reasonable body of evidence is available to guide practice, practice variation is common in nephrotic syndrome. The available evidence base for treatment of first presentation and relapses of nephrotic syndrome were synthesized and published in several systematic reviews, local guidelines,^{2,40,41} and also in a recent international clinical practice guideline.⁴² Nevertheless, lack of consensus regarding best treatment approaches is a well-known international phenomenon. Variation in care was documented in surveys of American pediatric nephrologists in 2000 and 2009; however, little has been done to address this problem in the United States or elsewhere.^{20,21} We performed a similar survey which was sent to all Canadian pediatric nephrologists (n=58) and achieved a 69% response rate. The results showed significant variation in steroid protocols and also in the choice of steroid sparing drugs and biopsy practices (see manuscript attached, [name] S, *Pediatr Nephrol* 2013). The total duration of steroid therapy ranged from a minimum of 7.5 weeks to a maximum of 26 weeks (median 16 weeks) for first presentation of nephrotic syndrome – likely contributing to considerable variation in cumulative steroid exposure among patients who may otherwise have similar clinical presentations. Sample protocols used by Canadian physicians and centres are shown in Appendix Tables 1a and 1b. The overall impact of this variability in steroid exposure on relapse rates of Canadian children with nephrotic syndrome has not been formally assessed and remains the most important and compelling unanswered question.

2.5 Patient-, physician- or centre-related factors may be associated with practice variation in nephrotic syndrome. Physicians make decisions about dose and duration of therapy while considering both efficacy and toxicity of drugs in the context of individual patient clinical presentations and preferences. Physicians may also be influenced by their training background, familiarity with the literature, and their work environments. In our survey of practice patterns, duration of steroid therapy prescribed was associated with year of graduation for physicians (i.e. years in practice) and the presence or absence of a standardized protocol in centres⁴³ – providing preliminary evidence that physician and centre-specific factors also play a role in variation of care. We also found widespread variation in the choice of second line agents – likely driven by beliefs regarding efficacy of each agent compared to toxicity. For example, we know anecdotally that many Canadian pediatric nephrologists avoid using cyclophosphamide, a well studied and effective drug for frequently relapsing and steroid dependent nephrotic syndrome due to risk of infertility and cancer, and prefer using tacrolimus a less well studied drug with a more favorable side effect profile.^{22,44} Therefore, understanding ‘why there is practice

variation' is a key step to overcome barriers to implementation of best practice approaches across many centres. No study to date has assessed reasons for variation in nephrotic syndrome care.

[figure not shown]
2.6 There is uncertainty in the literature regarding best treatment protocols for childhood nephrotic syndrome. The evidence supporting many guideline recommendations for steroid therapy and second line agents are based on small numbers of randomized controlled trials (RCTs), some with very few patients – leading to lack of trust among the physician groups in the robustness of the literature.^{44,45} In addition, the literature continues to evolve with conflicting messages. Three recent RCTs (2 in the same January 2015 *Kidney International* issue) were published; they all suggest that there is no benefit to prolonged steroid treatment of up to 6 months compared to 3 months for first presentation of nephrotic syndrome.⁴⁶⁻⁴⁸ A recent editorial published with these new RCTs suggest that future trials should no longer just focus on duration of steroid therapy over the short term, but rather study emerging novel treatments for nephrotic syndrome and long term outcomes.⁴⁵ In the light of new evidence, and prevalent practice variation, we believe that a national observational cohort study is *a necessary first step* to obtain valuable generalizable data. These data will: 1) inform whether there is a need to develop standardized protocols to reduce practice variation by identifying differences in patient outcomes based on steroid prescribed; 2) provide observational patient outcome data to complement interpretation of published short term clinical trial results; and 3) assist in strategic prioritization of future clinical trial questions regarding new and old therapeutics.

2.7 We need a collaborative research network and data infrastructure to improve outcomes in childhood nephrotic syndrome, a rare pediatric chronic disease. Childhood nephrotic syndrome is one of the most common acquired kidney diseases in children, but, it meets the Canadian Institutes for Health Research (CIHR) definition of a 'rare' disease (affects one person out of 2,000 or fewer).⁴⁹ No single centre or region in Canada has sufficient patient numbers to produce generalizable knowledge regarding effective treatments, the most significant barrier to generating high quality evidence and one that can be overcome by multi-centre collaborative studies. Clinical research networks, with the combination of high quality data and large sample size accrual, are proven powerful tools to improve health outcomes of children with rare diseases. For example, the ImproveCareNow network for pediatric inflammatory bowel disease includes 445 pediatric gastroenterologists and 50 sites, and has seen remission rates for Crohn's disease and colitis improve from 49% to 78% in just 5 years.⁵⁰⁻⁵² For steroid sensitive nephrotic syndrome in particular, there is a severe lack of well characterized clinical and/or research cohorts. There is only one single-centre cohort study in Canada documenting outcomes of steroid sensitive patients (INSIGHT study, with a focus on genetic investigations)⁵³ – creating a major gap in knowledge regarding overall quality of clinical care and patients' clinical progression and outcomes. Funding this proposal will sustain a national network, composed of >20 investigators, with an estimated 50 physicians who will enroll from 13 sites, and establish the *only* national longitudinal observational cohort study for children with nephrotic syndrome.

2.8 Expected results and significance: We expect to observe differences in relapse rates based on steroid prescribed (Objective 1) and we expect to find that physician and centre characteristics play an important role in determining variation in treatment protocols (Objective 2). Our KT strategies will utilize the collective information gathered in this study regarding steroid prescribed and relationship to outcomes, and factors determining variation in treatments, to develop best practice approaches for treatment of nephrotic syndrome, and to identify physicians and centres most or least likely to implement these approaches. This project will also provide the unprecedented opportunity for every child with nephrotic syndrome and every physician treating children with nephrotic syndrome to be enrolled into the observational cohort, their data being used to inform development, implementation and iterative refinement of treatment protocols, and provide foundational clinical data to prioritize future clinical trials.

